In the quality of life companion, patients will be assessed by multiple HRQOL (Health-related quality of life) scales at baseline, 3, 5, 7, 12, 26 and 52 weeks (see [Table 1](#) for details). Investigators are interested in evaluating the change of quality of life assessments from baseline to multiple time points during and after treatment and comparing the differences of such changes between treatment regimens. It is expected that patients in arm 1 (45 Gy) experience worse physical and functional well being, worse esophagitis than those in the remaining study arm (arm 2 or 3), and that patients in arm 2 (70 Gy) experience worse treatment inconvenience than those in arm 1 (45 Gy) or arm 3 (61.2 Gy). The HRQOL scores changed from baseline to 12 week are of the primary scientific interest. The size of the HRQOL companion is chosen such that one has adequate power to test three sets of scientific hypotheses as shown in Table 2). The companion will register 415 patients (57%) from the 729 patients consenting to the main treatment study. Of the 415 patients, 394 patients are expected to meet the eligibility criteria. Of the 394 patients on the companion study, 188 patients are expected in each of the two remaining study arms and 18 patients are in the discontinued study arm.

Table 2
Quality of Life Assessment

QoL Endpoint Variable	Hypothesis	Measure	Statistical Analysis

Primary Endpoints Physical Well-being, Functional Well-Being, Lung Cancer physical symptoms
 
FACT Esophageal Eating and Swallowing Subscales
	
Hypothesis A: At 12 weeks after the start of XRT, patients in the 45Gy arm will report worse physical symptoms and functioning than those in the high dose daily (70Gy) and concomitant boost RT (61.2 Gy) groups.
	
FACT-L (TOI)
 
FACT Esophageal Eating and Swallowing Subscales
	
Continuous scores/outcomes
 
T test; Analysis of covariance; Linear mixed effect model or general linear model with generalized estimating equations

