The following assumptions are made in the power calculations: (1) Based on the literature and previous CALGB studies, we expect that at least 80% of eligible patients who register to the companion will complete the HRQOL assessments at both baseline and 12 weeks after the start of radiation therapy. That is, of the 394 eligible patients on the companion study, 150 patients in the two remaining study arms and 15 in the discontinued study arm will have complete HRQOL assessments at both baseline and 12 weeks after the start of radiation therapy; (2) Within each set of hypothesis (A, B, C), Type I error will be controlled at the level of 0.05. The Bonferroni method is used to address the issue of multiple comparisons for simplicity and reasonable performance with a small number of comparisons; and (3) Two-sided tests will be used.

Hypothesis A

Three planned comparisons will be made to address Hypothesis A. The total TOI score from FACT TOI, the eating score and the swallowing score will be calculated from the FACT-Esophagus Subscale. The change scores between baseline and 12 weeks after the start of radiation therapy are of interest. A size of 150 patients with complete assessments at baseline and 12 weeks after the start of radiation therapy in each of the two remaining arms will have 85% power to detect an effect size of 0.397 s.d. unit on the scale of change score using a two group t-test at a significance level of 0.0167 (0.05/3). The effect size of 0.397 s.d. is usually associated with a moderate effect in quality of life literature.

Hypothesis B

Five comparisons will be made to address this hypothesis - ECOG esophagitis score (severe/ ≥ 7 vs moderate/ < 7), difficulty swallowing (severe/ ≥ 4 vs. moderate/ < 4), HADS depression score, HADS anxiety score, and quality-adjusted life year (QALY).

The ECOG esophagitis score ranges from 0 to 12 points. We will define patients with scores of ≥ 7 as “Severe” and score < 7 as “Moderate.” With 150 patients in each remaining arm with complete assessments at baseline and 12 weeks after the start of radiation therapy, a two group continuity corrected Chi-square test at a 2-sided significance level of 0.01 (0.05/5) will have 80% power to detect the 18% difference of the proportions of patients with severe symptoms between the two remaining study arms, assuming 35% of patients in arm 1 report severe symptoms and 17% in the other remaining arm (odds ratio of 2.625).

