Analytic Methods:

For continuous HRQOL (Health-Related Quality of Life) scores, including Physical Well-Being, Functional Well-Being, Lung Cancer Physical Symptoms subscale scores from the FACT-TOI, Eating and Swallowing subscale scores from the FACT-Esophagus Subscale, and depression and anxiety subscale scores from HADS, two-group t test and analysis of covariance will be the primary method used to analyze and test the planned comparisons for the change scores from baseline to 12 weeks after the start of radiation therapy with and without adjusting for other prognostic factors. In analysis of covariance, in addition to study arm, significant baseline prognostic factors will be included in the model to adjust for confounding effects. These planned tests results will be reported at the significance level designated in the section of power analysis. Similar exploratory univariate analyses will be conducted for the change score from baseline to other assessment points at 3, 5, 7, 26, and 52 weeks after the start of radiation therapy. Multivariate analyses for evaluating the trend of HRQOL scores varying over time will be conducted using a linear mixed effect model and linear model with generalized estimating equation (GEE) with all valid measures from multiple time points included in the analysis.

For binary dichotomized endpoints, such as ECOG esophagitis severity (severe/ ≥ 7 vs moderate/ < 7), difficulty swallowing (severe/ ≥ 4 vs. moderate/ < 4) and ordinal endpoints, such as treatment inconvenience (inconvenient/ ≤ 2 yes vs. convenient/ ≥ 3), Chi-square test and generalized linear model with a logit or multi-logit link will be used to test the planned comparisons. In regression analysis, baseline prognostic factors besides study arm will be included. Again, these planned tests will be reported at the significance level as designated in the section of power analysis. Similar multivariate analyses for evaluating the trend of HRQOL scores varying over time will be conducted using a nonlinear mixed effect model and generalized linear model with generalized estimating equation (GEE) with all valid measures from multiple time points included, in which logit link for dichotomized scores and multi-logit link for ordinal scores will be specified. In the analysis of ordinal scores, proportional odds assumptions will be tested.

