It is expected that a proportion of quality of life data collected at follow-up assessments will be missing due to various reasons, including failing health of patients. However, the percentage is expected to be less than 10% above and beyond that missing due to death. If the dominant missing mechanism is missing completely at random (MCAR) above and beyond the effect of study condition assignment, then the results based on complete data analysis will be unbiased. However, sensitivity analyses using different statistical methods and assuming different missing mechanisms (MCAR, MAR and NMAR) will be used to evaluate the robustness of main study findings from multivariate data analyses.

The quality-adjusted overall survival will be calculated for each study arm based on the utility score from EQ-5D and the subgroup difference will be tested using the method developed by Zhao and Tsiatis [93].

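### The primary week-12 quality-of-life tests are complete-case, and their only stated justification is a conditional MCAR statement that sits poorly with the failing-health dropout the plan expects

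*Combined protocol and SAP*

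**What the plan says.** All of this is in section 15.7 of the combined protocol and SAP unless noted.

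- **Time point.** The overview states: "The HRQOL scores changed from baseline to 12 week are of the primary scientific interest".
- **Primary method.** Analytic Methods covers the continuous scores (TOI components, Eating, Swallowing, HADS anxiety and depression) and takes week 12 as the end point of the change. It says: "two-group t test and analysis of covariance will be the primary method used to analyze and test the planned comparisons for the change scores".
- **Numbers.** The overview says "188 patients are expected in each of the two remaining study arms". The power section expects that "at least 80% of eligible patients who register to the companion will complete the HRQOL assessments" at both baseline and week 12, and bases Hypothesis A on "A size of 150 patients with complete assessments at baseline and 12 weeks after the start of radiation therapy" in each arm.
- **Longitudinal models.** Analytic Methods plans to evaluate trends over time "using a linear mixed effect model and linear model with generalized estimating equation (GEE) with all valid measures from multiple time points included". Table 2 also lists a linear mixed model or GEE, after the t test and ANCOVA, in the rows for the week-12 hypotheses on TOI, Eating, Swallowing and HADS.
- **Missing data.** Some follow-up data "will be missing due to various reasons, including failing health of patients", with less than 10% expected beyond losses to death. If the dominant mechanism is MCAR apart from any effect of assigned arm, then "the results based on complete data analysis will be unbiased". The next sentence plans sensitivity analyses under MCAR, MAR and NMAR, to check the robustness of findings from the multivariate analyses.
- **Reasons.** Section 10.2.3 has Form C-419 record why each missed assessment was missed.

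**The concern.** A change score needs both ends, so a patient without a week-12 form drops out of the primary test even when week 3, 5 and 7 scores are on file (the section 6.2 table collects all of these scales at those visits). The only reasoning given for relying on completers is the MCAR condition. Failing health is close to what TOI measures, so losses for that reason depend on the outcome and do not fit the condition, even within arm.

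If such losses differ between arms, in number or in kind, the primary quality-of-life contrast is biased. A difference is plausible here. Hypotheses A and B predict worse symptoms and esophagitis on 45 Gy, and week 12 falls 9 weeks after the end of radiotherapy on 45 Gy but 5 weeks after on 70 Gy (section 10.2.2). A likelihood-based model that uses the earlier scores needs only MAR. The plan already contains such a model but does not give it the lead.

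**Working it through.** **Inputs from the documents.** 188 eligible per arm; 80% completion; 85% power at 0.397 SD with two-sided alpha 0.0167 (Hypothesis A) and at 0.419 SD with alpha 0.01 (HADS), all in section 15.7; exponential survival with medians of 23 and 29.9 months (section 15.3).

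**Assumed, not in the documents.** The gap g, in SD, by which patients without week-12 data score worse than completers, and the split of missingness between arms.

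**Step 1: the plan's own figures.** 188 × 0.80 = 150.4, the stated 150. For Hypothesis A, 0.397 × √(150/2) = 3.438; less the critical value 2.393 this is 1.045, and Φ(1.045) = 0.852. The noncentral t with 298 df gives 0.848. The stated 85% reproduces, and it rests on completers only. For HADS at 0.419 SD and alpha 0.01 the noncentral t gives 0.849, also as stated.

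**Step 2: deaths by week 12.** 84 days / 30.4375 = 2.760 months.
- 45 Gy: 1 − 2^(−2.760/23) = 8.0%
- 70 Gy: 1 − 2^(−2.760/29.9) = 6.2%

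The difference is 1.8 points. Week 12 is counted from the start of radiotherapy and survival from randomization. For patients starting radiotherapy one 21-day cycle later, 15 weeks (105/30.4375 = 3.450 months) gives 9.9% and 7.7%, a difference of 2.2 points. Adding just under 10% for other reasons to the 12-week figures gives at most about 16% to 18%, which agrees with at least 80% completion.

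**Step 3: bias of the completer contrast.** If a fraction m is missing and those patients are g SD worse than completers, the completer mean exceeds the whole-arm mean by m × g. The bias in the arm difference is therefore m₁g₁ − m₂g₂, or g × (m₁ − m₂) when the gap is the same in both arms. Type I error is Φ(b/se − 2.393) + Φ(−b/se − 2.393), with n = 188(1 − m) per arm and se = √(1/n₁ + 1/n₂).

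| Missingness | Bias, g = 0.5 | Bias, g = 1.0 | Type I error (nominal 0.0167) |
|---|---|---|---|
| 20% and 20%, same gap | 0 | 0 | 0.0167 |
| Arms differ by 1.8 points | 0.009 SD | 0.018 SD | not computed |
| 18% and 22% | 0.020 SD | 0.040 SD | 0.018 to 0.023 |
| 15% and 25% | 0.050 SD | 0.100 SD | 0.027 to 0.064 |

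Worked case for 15% and 25% with g = 1.0: n = 159.8 and 141, se = 0.1155, b/se = 0.866, type I error 0.064. If 45 Gy is the arm losing 25%, power at a true 0.397 SD falls to 0.73 (g = 0.5) or 0.57 (g = 1.0). If 70 Gy loses 25%, power rises to 0.93 or 0.97 because the estimate is inflated.

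Equal rates do not guarantee safety: at 20% in each arm, gaps that differ by 0.5 SD give 0.20 × 0.5 = 0.10 SD.

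Against the powered effect, 0.018/0.397 = 4.5% and 0.10/0.397 = 25%.

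**The case against.** The defence of the plan is substantial.

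- **MCAR is not asserted.** The sentence begins with a condition, failing health is one of several reasons, and sensitivity analyses under three mechanisms follow at once. This stands. The weakness is that they are aimed at the multivariate findings, no NMAR method is named, and the week-12 test is not mentioned.
- **The mixed model is tied to the week-12 hypotheses in Table 2.** True. But Analytic Methods gives primacy to the t test and ANCOVA, uses the mixed model for trend, and specifies no week-12 contrast from it at the designated alpha.
- **Strict MCAR is not needed.** The condition lets missingness depend on arm, and a complete-case ANCOVA tolerates dependence on covariates in the model. This also stands, but arm and baseline factors do not capture health that fails after baseline.
- **A mixed model is not a cure.** It implicitly carries quality of life past death. With baseline as a covariate it still loses patients without a baseline score. No full assessment falls between weeks 7 and 12, so a decline in that interval that causes a missed form remains NMAR. All of this stands and limits what the change can achieve.
- **The larger bias figures are assumed.** Also true. With non-death losses below 10%, a 10-point difference would put nearly all of them in one arm.

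**Conclusion.** The point holds as a weakness in the choice of lead analysis. The primary week-12 tests of TOI, Eating, Swallowing and HADS are complete-case by construction, and the only support given is a conditional statement that fits poorly with the expected reason for loss.

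The size is modest and conditional. It is zero if missing rates and gaps match across arms. With gaps of 0.5 to 1.0 SD it is about 0.01 to 0.02 SD for a differential as large as the one in deaths that the design medians imply, and up to 0.10 SD for an assumed 10-point differential. The documents fix neither the gap nor the non-death differential, and no direction is shown. The death-based figure indicates scale only, since scores after death are undefined.

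A reader might infer three stronger things that the documents do not support:
- **That the plan contradicts itself by asserting MCAR.** It states a condition and then plans for its failure.
- **That the mixed model serves only to describe trends.** Table 2 lists it against the week-12 hypotheses.
- **That a quarter of the powered effect is at risk.** That figure needs the largest assumed gap and the largest assumed differential together, or equal rates with gaps 0.5 SD apart.

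Overall survival is not touched. Neither is the QALY comparison, which has its own quality-adjusted survival test.

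**What to change.** 1. Make the primary test for TOI, Eating, Swallowing and the two HADS scores the week-12 arm contrast from a likelihood-based repeated-measures model on the post-baseline scores through week 12 (weeks 3, 5, 7 and 12). Include baseline score, visit, arm and arm-by-visit. Keep the existing alpha: 0.0167 per test for Hypothesis A and 0.01 for HADS. Do not use unweighted GEE for this purpose, since it is generally not valid under MAR.
2. Keep the complete-case t test and ANCOVA as sensitivity analyses.
3. Name the NMAR method, apply it to the same week-12 contrast, and inform it with the reasons recorded on Form C-419.
4. Report deaths before week 12 and missing baselines by arm beside the estimate, and interpret it in that light, because the model resolves neither.

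**Cost.** No new patients or data are needed, and the model class is already in the plan. The change is cheap rather than free: it amends the named primary method of a substudy closed to accrual since August 30, 2017. A patient registered that day, starting treatment within 7 days and radiotherapy one 21-day cycle later, would reach week 12 after 7 + 21 + 84 = 112 days, in December 2017. The current text already describes procedures from March and April 2018, so the week-12 data are probably in hand. The amendment should therefore be made, and dated, before quality-of-life results are examined by arm, to avoid the criticism that the method was chosen after the fact.

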15.8 CDUS Reporting

The Alliance Statistics and Data Center will submit quarterly reports to CTEP by electronic means using the Clinical Data Update System (CDUS).

16.0 ADVERSE EVENT REPORTING (AER)

Investigators are required by Federal Regulations to report serious adverse events as defined below. Investigators are required to notify the Alliance Central Office, the Study Chair, and their Institutional Review Board (IRB) if a patient has a reportable serious adverse event. The descriptions and grading scales found in the revised NCI Common Terminology Criteria for Adverse Events (CTCAE) version 5.0 will be utilized for serious AE reporting beginning April 1, 2018. This study will utilize version 4.0 for routine toxicity reporting. All appropriate treatment areas should have access to a copy of the CTCAE version 5.0. A copy of the CTCAE version 5.0 can be downloaded from the CTEP web site [REDACTED]. All reactions determined to be “reportable” in an expedited manner must be reported using the NCI Adverse Event Expedited Reporting System (CTEP-AERS).

16.1 CALGB 30610 Adverse Event Reporting Requirements

Phase 2 and 3 Trials: CTEP-AERS Expedited Reporting Requirements for Adverse Events That Occur Within 30 Days¹ of the Last Dose of Treatment

	Grade 1	Grade 2	Grade 2	Grade 3		Grade 3		Grades 4 & 5 ²	Grades 4 & 5 ²
	Unexpected and Expected	Unexpected	Expected	with Hospitalization	without Hospitalization	with Hospitalization	without Hospitalization	Unexpected	Expected
Unrelated Unlikely	Not Required	Not Required	Not Required	Not Required	Not Required	Not Required	Not Required	10 Calendar Days	10 Calendar Days
Possible Probable Definite	Not Required	Not Required	Not Required	Not Required	Not Required	Not Required	Not Required	10 Calendar Days	10 Calendar Days

¹ Adverse events with attribution of possible, probable, or definite that occur greater than 30 days after the last dose of treatment require reporting as follows:

CTEP-AERS 10 calendar day report:

- Grade 4 unexpected events
- Grade 5 expected or unexpected events

March 2005

Note: All deaths on study require both routine and expedited reporting regardless of causality. Attribution to treatment or other cause should be provided.

- Expedited AE reporting timelines defined:
 - "10 calendar days" - A complete CTEP-AERS report on the AE must be submitted within 10 calendar days of the investigator learning of the event.
- Any event that results in persistent or significant disabilities/incapacities, congenital anomalies, or birth defects must be reported via CTEP-AERS.

- Use the NCI protocol number and the protocol-specific patient ID provided during trial registration on all reports.

16.2 Additional Instructions or Exclusions from CTEP-AERS Expedited Reporting Requirements:

- Death due to progressive disease should be reported as Grade 5 “Disease progression” in the system organ class (SOC) “General disorders and administration site conditions.” Evidence that the death was a manifestation of underlying disease (*e.g.*, radiological changes suggesting tumor growth or progression: clinical deterioration associated with a disease process) should be submitted.

Any death occurring within 30 days of the last dose, regardless of attribution to the investigational agent/intervention requires expedited reporting within 24 hours.

Any death occurring greater than 30 days after the last dose of the investigational agent/intervention requires expedited reporting within 24 hours only if it is possibly, probably, or definitely related to the investigational agent/intervention.

- All grade 4 events that are unexpected and that are at least possibly related to treatment must be reported via CTEP-AERS within 10 calendar days.
- Grade 4 events that are expected do not require CTEP-AERS expedited reporting, even if they result in hospitalization.
- Adverse events include those listed in [Section 11.0](#) and in the package inserts.
- All adverse events reported via CTEP-AERS (*i.e.*, serious adverse events) should also be forwarded to your local IRB.
- The reporting of adverse events described in the table above is in addition to and does not supplant the reporting of adverse events as part of the report of the results of the clinical trial, *e.g.*, study summary forms or cooperative group data reporting forms (see [Section 6.1](#) for required CALGB forms).
- Pregnancy loss is defined in CTCAE as “Death in utero.” Any Pregnancy loss should be reported expeditiously, as Grade 4 “Pregnancy loss” under the Pregnancy, puerperium and perinatal conditions SOC. A Pregnancy loss should NOT be reported as a Grade 5 event under the Pregnancy, puerperium and perinatal conditions SOC, as currently CTEP-AERS recognizes this event as a patient death.

A neonatal death should be reported expeditiously as Grade 4, “Death neonatal” under the General disorders and administration SOC.

- All new malignancies must be reported via CTEP-AERS whether or not they are thought to be related to either previous or current treatment. All new malignancies should be reported, *i.e.* solid tumors (including non-melanoma skin malignancies), hematologic malignancies, myelodysplastic syndrome/acute myelogenous leukemia, and *in situ* tumors. In CTCAE version 5.0, the new malignancies (both second and secondary) may be reported as one of the following: (1) Leukemia secondary to oncology chemotherapy, (2) Myelodysplastic syndrome, (3) Treatment-related secondary malignancy, or (4) Neoplasms benign, malignant and unspecified-other. Whenever possible, the CTEP-AERS reports for new malignancies should include tumor pathology, history or prior tumors, prior treatment/current treatment including duration, any associated risk factors or evidence regarding how long the new malignancy may have been present, when and how the new malignancy was detected, molecular characterization or cytogenetics of the original tumor (if available) and of any new tumor, and new malignancy treatment and outcome, if available.

